# ClinicalTrials.gov Final Outcomes Report

NCT Number:	05103384
Project Title:	Utilizing Neural Signatures and Virtual Reality to Advance DBS Programming
Principal Investigator Name:	[name]
Principal Investigator Organization and Address:	Cleveland Clinic [name]
Document Date:	9/27/2023

**Title:** Utilizing Neural Signatures and Virtual Reality to Advance DBS Programming

**Primary Investigator:** [name]

**Study Funder:** Michael J. Fox Foundation for Parkinson's Research

**Protocol Date:** 9/27/2023

**PROJECT GOAL:** Falls related to postural and gait impairments and freezing of gait (FOG) occur in nearly 80% of Parkinson's disease (PD) patients and are the greatest motor-related contributor to health care costs and the primary reason for transition to dependent care settings among PD patients. Despite their prevalence in the daily lives of PD patients, identifying FOG episodes in a clinical or laboratory environment is challenging. Consequently, the neural signature underlying FOG remains elusive. A necessary step in treating FOG is characterizing neural activity within the basal ganglia during FOG episodes. An approach to evaluate the neural signals associated with FOG includes recording the neural activity in the area of the subthalamic nucleus (STN) or globus pallidus internus (GPi) from implanted deep brain stimulation (DBS) leads. The proposed project combines the most advanced virtual reality (VR) technology and neural recording techniques to identify specific neural correlates of FOG while patients physically walk through a virtual environment, Virtual-Gait Task (V-GAIT), that simulates motor and cognitive\limbic triggers.

**Objective:** To identify the corresponding neural signatures of FOG associated with motor and cognitive\limbic triggers.

Fifteen individuals with PD will complete the V-GAIT modules while synchronized kinematic and neural data from the DBS lead within the STN or GPi are recorded. The kinematic data will be utilized to identify the timing of FOG episodes in the neural data. The neural correlates of FOG in the ON and OFF medication states within each domain will be evaluated.

## METHODOLOGY AND APPROACH

The V-GAIT platform utilizes a VR headset to deliver high fidelity realistic virtual environments resembling a home environment while the participant walks on an omnidirectional treadmill. Briefly, the VR headset provides a realistic display with high resolution and refresh rate, wide field of view, and color clarity currently available. The 360-degree moving platform allows the user to naturally walk and turn in any direction. The 3-dimensional linear and angular position of the head, waist, and both feet are tracked using motion sensors that are embedded in the headset, waist belt, and foot straps. To ensure safety, a supported harness is worn by the user. To monitor overall exertion and provide a proxy for stress, a heart rate monitor is integrated into the V-GAIT platform.

**V-GAIT Module:** This module replicates a home, including a kitchen. The tasks will include, but not be limited to, walking in hallways will have digital doorways which reduce the width of the passageway and a virtual room where participants will appear to walk on an elevated platform to trigger anxiety-induced FOG.

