## **DATA ANALYSIS**

**Biomechanical Data Analysis:** All data will be recorded and analyzed off-line using custom-scripts in Matlab using the Chronux toolbox to examine changes in oscillatory neural activity time-locked to FOG episodes identified with the kinematic data from the body worn motion sensors in the motion capture area. The 3D position data of each foot will be utilized to determine steps and other biomechanical stepping variables FOG episodes will be identified utilizing the data from the body-worn motion sensors.

**Neural Data Analysis:** Neural data will be detrended and passed through a moving window line noise subtraction algorithm to remove drifting baseline and continuous noise artifacts, respectively. From the Percept device, 6 electrode pair combinations, 3 combinations per DBS lead, will be recorded directly with the Percept communicator. Windows containing movement artifacts will be visually identified by large fluctuations in the time series and high amplitude broadband activity in the spectrogram and removed from further analysis. Triggered spectrograms will be calculated for each trial using the multi-taper method with a 100 ms, 50 ms overlap moving window, 2.5 Hz frequency resolution, and 1 taper.

**Local Field Potential (LFP) Outcomes:** The relationship of synchronization and desynchronization changes in oscillatory activity within the delta, theta, alpha, beta and/or gamma bands as well as the power of high-frequency oscillations (200+ Hz) will be calculated in relation to all events identified with the kinematic data, i.e. normal walking and FOG episodes. Power spectral densities will be used to determine the power and confidence bands of oscillatory activity across frequencies during these events.

**Statistical Analysis:** Neural data outcomes, average power within alpha, beta, and/or gamma frequency bands, will be quantified using descriptive statistics during FOG episodes and during periods of functional walking while performing the V-Gait modules. Within and across participant analyses will determine the degree of consistency and similarity of the neural signal during FOG episodes between each medication state (ON and OFF).

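### Turning is free and its data are recorded, but the FOG-versus-walking contrast does not separate it, so turning could confound the contrast by an unknown amount and in an unknown direction.

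*Combined protocol and SAP*

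**What the plan says.** METHODOLOGY AND APPROACH describes the treadmill: "The 360-degree moving platform allows the user to naturally walk and turn in any direction". On measurement it says "The 3-dimensional linear and angular position of the head, waist, and both feet are tracked using motion sensors". The tasks named there are hallways narrowed by doorways and a raised walkway. The list is left open, and turning is not named as a task.

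Under DATA ANALYSIS, Biomechanical Data Analysis gives the foot data one purpose: "The 3D position data of each foot will be utilized to determine steps and other biomechanical stepping variables". No section assigns a use to the angular data. LFP Outcomes relates oscillatory power to events, "in relation to all events identified with the kinematic data, i.e. normal walking and FOG episodes". Statistical Analysis says that average band power "will be quantified using descriptive statistics during FOG episodes and during periods of functional walking while performing the V-Gait modules". Neither normal nor functional walking is defined, so the reader cannot tell whether turns without freezing belong to the reference windows.

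Two other provisions might bear on the point. The Objective splits the evaluation by medication state and trigger domain: "The neural correlates of FOG in the ON and OFF medication states within each domain will be evaluated". Neural Data Analysis removes some windows: "Windows containing movement artifacts will be visually identified by large fluctuations in the time series and high amplitude broadband activity in the spectrogram".

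**The concern.** Turning and straight walking are different motor tasks, and participants can do either at any moment in a freely explored home scene. A comparison of mean power between FOG windows and walking windows is a clean contrast of freezing only if the two sets have a similar mix of turning, or if turning leaves power unchanged. The plan secures neither.

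The stated aim is to find neural correlates specific to FOG. If the mix differs and turning alters power, part of what is reported as a FOG signature would reflect the movement under way. The planned strata do not prevent this, because a person can turn and walk straight within one medication state and one trigger domain. Artifact removal does not prevent it either, because it is judged from the look of the signal and not from direction of travel.

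**Working it through.** **Inputs from the documents.** Two event classes (LFP Outcomes, Statistical Analysis); 15 participants (INCLUSION/EXCLUSION CRITERIA); angular position recorded (METHODOLOGY AND APPROACH). The plan gives no effect size, SD, power or test, so it has no figure of its own to reproduce.

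**Inputs that must be assumed.**
- pF and pW: the shares of FOG and walking windows that fall in turns (for FOG, episodes that began in a turn).
- T: the power difference between turning and straight walking without freezing, in SD of the paired FOG-minus-walking differences.
- k: the fraction of T still present once a freeze has begun.
- d: the true effect of freezing.

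**Step 1, formula.** With straight-walking power m, the FOG mean is m + d + k × pF × T and the walking mean is m + pW × T. The contrast is d + (k × pF − pW) × T, so the bias is (k × pF − pW) × T. If turning-related power persists in full (k = 1), this is (pF − pW) × T, which is zero when pF = pW or T = 0. If a freeze abolishes it (k = 0), the bias is −pW × T.

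**Step 2, numbers with T = 0.5 SD.**

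| pF | pW | k = 1: (pF − pW) × 0.5 | k = 0: −pW × 0.5 |
|---|---|---|---|
| 0.30 | 0.10 | 0.10 | −0.05 |
| 0.50 | 0.15 | 0.175 | −0.075 |
| 0.70 | 0.20 | 0.25 | −0.10 |
| 0.20 | 0.20 | 0 | −0.10 |
| 0.10 | 0.20 | −0.05 | −0.10 |
| 0.50 | 0 | 0.25 | 0 |

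The first three rows assume that freezes favour turns. The next two show that equal shares or the opposite ordering give zero or negative values. The last row is the case where reference walking means straight walking only.

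**Step 3, scale.** The 95% half-width for a mean paired difference at n = 15 is t(0.975, 14)/√15 = 2.145/3.873 = 0.554 SD. The plan promises no such interval; it serves here only as a yardstick. Every value in the table is below half of it (0.277).

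**Step 4, does separating the classes help?** For k = 1, d = 0, T = 1, pF = 0.7 and pW = 0.2, the formula gives (0.7 − 0.2) × 1 = 0.50. A simulation of 4,000 runs with 40 windows per class gave 0.500 for the unadjusted contrast and 0.005 for the average of the within-turning and within-straight contrasts.

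For k = 0, the straight-onset contrast still equals d, but the turn-onset contrast equals d − T. Averaging the two with weights from the FOG windows gives a bias of −pF × T. At pF = 0.7, pW = 0.2 and T = 0.5 SD that is −0.35 SD, against −0.10 SD unadjusted. Separate contrasts are therefore informative under either assumption, but a single weighted estimate can be further from d than the unadjusted one.

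**The case against.** The strongest reply is that the premise is not in the documents. Nothing in them says that freezes cluster in turns or that turning alters the recorded power. The conditions described as provoking FOG are narrowed doorways and a raised walkway, and turning appears only as something the treadmill permits. This stands: the point is conditional, and neither size nor sign can be derived.

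A second reply is that a freeze may interrupt the turn, so the usual mixture formula need not apply. This also stands. It is why the k = 0 column is shown and why no weighted adjusted estimate is proposed.

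A third is sparseness. Two medication states, two trigger domains and two turning classes make 2 × 2 × 2 = 8 cells per participant, with an unknown number of freezes. This is fair, and pooling over domains reduces the cells to 2 × 2 = 4.

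A fourth is that the analysis is descriptive. This does not remove the point, because a descriptive mean difference carries the same bias as a tested one.

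A reader might go further and infer that turning would mimic a difference between ON and OFF medication. The documents do not support that. The same people complete V-GAIT in both sessions (RESEARCH DESIGN AND METHODS, Table 1), and nothing indicates that turning would differ between them.

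**Conclusion.** The gap is real but conditional. The plan permits and records turning, yet its FOG-versus-walking contrast neither separates nor balances it. Confounding follows if turning shares differ between the classes and turning changes power, with the added question of how much of that change survives a freeze.

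On assumed shares of 0.3 to 0.7 for FOG and 0.10 to 0.20 for walking, T = 0.5 SD and full persistence, the bias is 0.10 to 0.25 SD of the paired differences. That is inside the 0.55 SD half-width at n = 15. Unlike sampling error, it would not shrink with more participants. Other assumptions that fit the documents equally well give zero or a negative value.

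A reader might infer that the reported signature will be largely one of turning, or that it will be inflated. The documents support neither. What they support is a modest addition that lets the investigators check whether the signal is specific to freezing. The gap lies in the analysis text and not in data collection.

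**What to change.** **Biomechanical Data Analysis.** Using the waist yaw already recorded, set one yaw-rate threshold before any contrast is viewed and apply it in both sessions. Label walking windows as turning or straight, and label each FOG episode by whether it began in a turn. Say whether non-freezing turns count as normal or functional walking, and keep them as labelled windows either way.

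**Statistical Analysis.** Keep the unadjusted FOG-minus-walking figure. Add a sensitivity analysis, pooled over trigger domains, that reports:
- the turning share of each class;
- turn-onset FOG against non-freezing turns;
- straight-onset FOG against straight walking.

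Do not combine the two contrasts into one weighted adjusted estimate. State that a freeze may interrupt the turn, so the turn-onset contrast includes any loss of turning-related power.

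**Cost.** A few sentences of plan text and a scripted label, with no new data, visits or participant burden. Some participants will have freezes in only one class, so the separate contrasts will rest on fewer people and be less precise than the unadjusted one.

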## INCLUSION/EXCLUSION CRITERIA

**Participants:** Fifteen individuals with idiopathic PD will be recruited for the study. Individuals who have previously undergone DBS surgery with the Medtronic Percept BrainSense DBS system will complete the protocol while neural data from the DBS electrodes are streamed.

Inclusion Criteria:

- Clinical diagnosis of idiopathic PD
- Previous implantation of Percept DBS system as standard of care for their PD treatment

- Self-reported response of one or greater on question #3 of the FOG-Q
- Ability to ambulate independently for a minimum of 10 minutes
- Ability to provide informed consent

Exclusion Criteria:

- Neurological disease other than PD
- Musculoskeletal impairment that affects one's ability to ambulate for 15 minutes continuously
- Presence of active and untreated psychiatric symptoms meeting Diagnostic and Statistical Manual of Mental Disorders-4th Edition (DSM-IV) criteria for Axis-I disorder. Depression and anxiety are very common in patients with Parkinson's disease and are often mitigated as part of routine care. Depression and anxiety will not preclude study participation
- Cognitive impairment meeting Diagnostic and Statistical Manual of Mental Disorders-4th Edition (DSM-IV) criteria for dementia on formal neuropsychological evaluation
- Current alcohol or substance abuse
- Hearing or visual impairment precluding VR use
- Lack of fluency in English which may invalidate certain tests

## RESEARCH DESIGN AND METHODS

Individuals with the Medtronic Percept DBS system will be medically stable status post DBS surgery prior to enrollment.

**Screening:** Potential participants will be identified and screened by a member of the study team. They will undergo an in-person informed consent process. They will also complete a familiarization session with the VR headset and treadmill. The Percept system allows for continuous streaming of LFP data from the implanted device.

**V-GAIT Assessments:** Participants will perform two assessment sessions. During the sessions, the participants will complete the V-GAIT as outlined in Table 1. The sessions can be performed consecutively on the same day or on separate days depending on patient tolerance and preference.

Table 1: Assessment States		
	DBS State	PD Medication State
Session 1	Off	Off
Session 2	Off	On

## DATA COLLECTION PROCEDURES

**Neural Recording Procedures:** The proposed study design will enable synchronized recordings to be made in the form of LFP from the six or eight channels of implanted DBS lead(s), as well as IMU sensors from the V-GAIT platform to quantify gait-related behaviors using a commercial EEG recording platform. The physiological and sensor data will be synchronized to motor task and gait-related activities and events associated with participant performance on the V-GAIT paradigm through additional analog and digital ports using a low voltage electrical current (1.5 mA) through surface electrodes placed on the participant's neck.

**Behavioral Tasks:** The Unified Parkinson's Disease Rating Scale (UPDRS) will be conducted by a rater blinded to medication state.

## **DATA ANALYSIS**

**Biomechanical Data Analysis:** All data will be recorded and analyzed off-line using custom-scripts in Matlab using the Chronux toolbox to examine changes in oscillatory neural activity time-locked to FOG episodes identified with the kinematic data from the body worn motion sensors in the motion capture area. The 3D position data of each foot will be utilized to determine steps and other biomechanical stepping variables FOG episodes will be identified utilizing the data from the body-worn motion sensors.

**Neural Data Analysis:** Neural data will be detrended and passed through a moving window line noise subtraction algorithm to remove drifting baseline and continuous noise artifacts, respectively. From the Percept device, 6 electrode pair combinations, 3 combinations per DBS lead, will be recorded directly with the Percept communicator. Windows containing movement artifacts will be visually identified by large fluctuations in the time series and high amplitude broadband activity in the spectrogram and removed from further analysis. Triggered spectrograms will be calculated for each trial using the multi-taper method with a 100 ms, 50 ms overlap moving window, 2.5 Hz frequency resolution, and 1 taper.

**Local Field Potential (LFP) Outcomes:** The relationship of synchronization and desynchronization changes in oscillatory activity within the delta, theta, alpha, beta and/or gamma bands as well as the power of high-frequency oscillations (200+ Hz) will be calculated in relation to all events identified with the kinematic data, i.e. normal walking and FOG episodes. Power spectral densities will be used to determine the power and confidence bands of oscillatory activity across frequencies during these events.

**Statistical Analysis:** Neural data outcomes, average power within alpha, beta, and/or gamma frequency bands, will be quantified using descriptive statistics during FOG episodes and during periods of functional walking while performing the V-Gait modules. Within and across participant analyses will determine the degree of consistency and similarity of the neural signal during FOG episodes between each medication state (ON and OFF).

**Confidentiality:** CCF study investigators will have sole access to the study data. To protect confidentiality, participants' data will be identified only by coded subject number and stored in a secure location in a de-identified manner. A password-protected, electronic record linking subject numbers with identifying information will be maintained in a password-protected folder on a secure server and only CCF-based study investigators will have access to this file. Data analysis will be conducted by the study investigators in consultation with biostatistics, where appropriate. Dissemination of the results will largely involve aggregate data, although individual data points may be used where illustrative. All dissemination of the study findings will maintain confidentiality and include only de-identified data, except in the situation where express written permission has been obtained from the participant in advance.

**Adverse Events and Safety:** A Data Safety Monitoring Board (DSMB) will oversee this Phase I study. Non-conflicted members in the following areas: neurology, neurosurgery, statistics and bio-ethics will be recruited. Additionally, the Principal and Co-Investigators, along with the rest of the research team, will continuously monitor subject safety and data integrity. Adverse events and Unanticipated Problems will be reviewed by the Principle and Co-Investigators. If an Adverse Event occurs, it will be recorded on the Adverse Event Summary Sheet, and this will be submitted along with the Adverse Event Report in accordance with the stated time limitations. No clinical electrophysiological or imaging report will be generated as the experiments performed do not constitute diagnostic studies. However, if an unexpected finding is observed during the electrophysiological analysis, the appropriate clinical consults will be ordered.

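### The stated LFP cleaning has no check for cardiac (QRS) artefact; on a channel that carries it, alpha and beta contrasts can be biased if heart rate differs between the conditions compared

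*Combined protocol and SAP*

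**What the plan says.** All the cleaning is set out in DATA ANALYSIS, Neural Data Analysis, of the combined protocol and SAP. The two automatic steps are: "Neural data will be detrended and passed through a moving window line noise subtraction algorithm to remove drifting baseline and continuous noise artifacts, respectively". The third is manual: "Windows containing movement artifacts will be visually identified by large fluctuations in the time series and high amplitude broadband activity in the spectrogram", and those windows are dropped. No numeric threshold is given. The spectrograms then use a "100 ms, 50 ms overlap moving window, 2.5 Hz frequency resolution, and 1 taper". The channels are bipolar: "From the Percept device, 6 electrode pair combinations, 3 combinations per DBS lead, will be recorded directly with the Percept communicator".

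The Statistical Analysis paragraph names the outcome: "Neural data outcomes, average power within alpha, beta, and/or gamma frequency bands, will be quantified using descriptive statistics during FOG episodes", with the same summary during functional walking. It adds the medication comparison: "Within and across participant analyses will determine the degree of consistency and similarity of the neural signal during FOG episodes between each medication state".

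Heart rate appears only in METHODOLOGY AND APPROACH: "To monitor overall exertion and provide a proxy for stress, a heart rate monitor is integrated into the V-GAIT platform". That section also describes "a virtual room where participants will appear to walk on an elevated platform to trigger anxiety-induced FOG". Neither the cleaning nor the analysis text uses the heart-rate data.

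**The concern.** A QRS complex is brief, recurs with each beat and is not caused by movement. Detrending removes slow drift and line-noise subtraction removes continuous noise, so neither is aimed at it. The visual step is aimed at movement and has no threshold. It may miss a QRS, or it may catch a large one and delete the windows around it.

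If the QRS stays in, measured band power on that channel is LFP power plus a term proportional to heart rate. A heart-rate difference between two conditions would then look like a change in oscillatory activity. For FOG versus walking the design makes such a difference plausible, because one virtual room is meant to provoke freezing through anxiety and heart rate is recorded as a marker of stress. With 15 participants and descriptive summaries only, no later step in the plan would expose a cardiac contribution, and an alpha or beta signature of FOG would remain open to that explanation.

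**Working it through.** The plan gives no artefact figure to reproduce. The check therefore asks whether the stated steps leave a QRS in the signal, and how much that could matter.

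**Inputs.** From the documents: the three cleaning steps, the 100 ms window with 50 ms overlap, and the alpha, beta and/or gamma outcome. Assumed: a 1/f LFP sampled at 250 Hz, a QRS about 100 ms wide, a QRS peak of A times the LFP SD, and the heart rates. The plan gives no band limits; alpha was taken as 8-12 or 8-13 Hz and beta as 13-30 Hz.

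**1. Where the energy falls.** For one pulse shape at widths of 80, 100 and 120 ms, the alpha share was 26%, 31% and 31%, and the beta share 36%, 18% and 7%. The two together are about 61%, 49% and 38%. A different 100 ms pulse gave 36% + 38% = 74%. Most of the rest falls in delta and theta. Gamma receives essentially none.

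**2. Survival.** After linear detrending and a 60 Hz notch (a stand-in for the line-noise algorithm), 98-100% of the artefact's alpha and beta power remained.

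**3. Bias formula.** Let c be the cardiac share of band power in the reference condition. With no true LFP change,

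relative change in power = c × (HR1/HR0 − 1).

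For 80 to 100 bpm the bracket is 0.25, so c = 0.10, 0.25 and 0.50 give +2.5%, +6.25% and +12.5%. For 80 to 90 bpm the bracket is 0.125, giving +1.25%, +3.1% and +6.25%.

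**4. Simulated false rise, 100 ms windows, no true change.** The last column scales the middle one by (75 − 70)/(90 − 70) = 0.25, because the formula is linear in heart rate.

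| A | 70 to 90 bpm, alpha / beta | 70 to 75 bpm, alpha / beta |
|---|---|---|
| 1 | about 2% / 1.5% | about 0.5% / 0.4% |
| 2 | about 6% / 5% | about 1.5% / 1.25% |
| 4 | about 15% / 14% | about 3.75% / 3.5% |

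Direct simulation of the 5 bpm step gave about 0.5-1%, 1-3% and 3-5% in one set of runs, and about 0.5-4% overall in another. The alpha figure is sensitive to pulse shape and windowing: other 100 ms runs for 70 to 90 bpm gave about 1%, 3-4% and 9-11%.

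**5. Equal heart rates.** Let K be the added cardiac power.

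- Difference: (FOG + K) − (walking + K) = FOG − walking, so there is no bias.
- Ratio: measured ratio = (1 − c) × true ratio + c. A true 1.30 reads as 0.75 × 1.30 + 0.25 = 1.225 at c = 0.25, and 0.50 × 1.30 + 0.50 = 1.15 at c = 0.50.

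**6. If QRS windows are deleted instead.** Share of windows touched = (window + QRS width) × bpm/60 = (0.1 + 0.1) × 70/60 = 0.233 at 70 bpm, and 0.2 × 90/60 = 0.30 at 90 bpm. With every such window deleted at A = 4, mean alpha and beta power stayed within 0.7% of truth at both rates. Deletion therefore costs data but does not itself bias mean power, provided heartbeat timing is unrelated to LFP power.

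**The case against.** The strongest reply is that the premise cannot be verified. The documents do not say that any channel carries cardiac voltage. The recordings are between electrode pairs, where differencing can reduce a distant source that both contacts share. The largest figures come from large QRS peaks, which are the ones most likely to be caught by eye, so they are nearer a ceiling than an expectation. FOG and walking occur in the same modules and session, so the heart-rate gap may be small. All of this stands, and it makes the point conditional. It does not supply a check: differencing need not remove the artefact, and a visual rule without a threshold cannot be relied on to do so.

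Three stronger readings are tempting, and the documents do not support them.

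- A reader might infer that both planned contrasts are biased. Contamination alone does not bias an absolute contrast; heart rate must also differ. The documents give no heart rates, and for ON versus OFF they give no reason to expect a difference.
- A reader might infer that a constant cardiac term shrinks a true FOG-walking difference. It cancels in a difference. It dilutes only a ratio or percent change, and the plan names neither.
- A reader might infer that the module is designed to change heart rate. The text says that one room is meant to trigger anxiety-induced freezing and that heart rate is monitored.

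**Conclusion.** The point holds in conditional form. The stated pipeline has no detection or removal of cardiac artefact, and the two automatic steps leave it almost intact in two of the three bands named for the outcome. If a channel is contaminated and heart rate differs between the compared conditions, alpha and beta power will show a false change: from about half a percent for a 5 bpm gap with a small QRS to about 15% for a 20 bpm gap with a QRS peak four times the LFP SD. FOG versus walking is the more exposed contrast; for ON versus OFF the documents provide neither a reason nor a figure.

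The sizes rest on the assumed LFP spectrum, pulse shape, amplitude and heart rates. The share of channels affected is unknown, so the effect on the study as a whole cannot be stated. The change is still worth making: it is cheap, and without it a reader cannot tell a clean channel from a contaminated one.

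**What to change.** In Neural Data Analysis, add a step before artefact rejection and spectrogram calculation:

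1. For each channel, detect R-peaks in the LFP itself and compute the R-peak-locked average. Use the heart-rate monitor only to confirm the rate, since the plan does not say that it gives beat-level timing.
2. Where that average exceeds a pre-specified threshold (for example, the 95th percentile of averages locked to random times), subtract the QRS template from that channel. Apply the same rule to all events and both medication states.
3. State that QRS windows are not to be deleted as movement artefact.
4. Repeat the alpha and beta FOG-walking and ON-OFF summaries without the channels that needed subtraction, and report how many there were.

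The cost is one added step in the existing Matlab scripts and one sensitivity table, with no new data or visits. The downsides are small: subtraction can remove a little true LFP around each R-peak, and the sensitivity summary uses fewer channels. If no channel crosses the threshold, the report can say so and the question is closed.

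### Movement-artifact windows are removed by eye with no stated masking to event or medication state, and the amount removed is not planned to be reported

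*Combined protocol and SAP*

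**What the plan says.** All of this is in the combined protocol and SAP.

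- **Cleaning rule (Data Analysis, Neural Data Analysis).** After detrending and line-noise subtraction, windows with movement artifact are "visually identified by large fluctuations in the time series and high amplitude broadband activity in the spectrogram and removed from further analysis". No numeric threshold is given. The triggered spectrograms are described next.
- **Outcome (Data Analysis, Statistical Analysis).** The neural outcome, "average power within alpha, beta, and/or gamma frequency bands, will be quantified using descriptive statistics during FOG episodes and during periods of functional walking". The same paragraph compares the FOG signal between the ON and OFF medication states.
- **Event labels (Data Analysis, Biomechanical Data Analysis and LFP Outcomes).** "FOG episodes will be identified utilizing the data from the body-worn motion sensors". Oscillatory changes "will be calculated in relation to all events identified with the kinematic data, i.e. normal walking and FOG episodes".
- **Masking (Data Collection Procedures, Behavioral Tasks).** The only masking stated anywhere is for a clinical scale: "The Unified Parkinson's Disease Rating Scale (UPDRS) will be conducted by a rater blinded to medication state".
- **Who analyses (Confidentiality paragraph).** "Data analysis will be conducted by the study investigators in consultation with biostatistics, where appropriate". The same paragraph gives the study investigators sole access to the data.

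No section states masking for the artifact step, a tally of removed windows, or a repeat of the analysis under another cleaning rule.

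**The concern.** Deciding which windows to drop is a judgement made on the same signal that supplies the outcome. A narrowband rise alone would not meet the criterion. High broadband power would, and it contains the alpha, beta and gamma bands, so selection and outcome are not independent.

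The two events compared, freezing and walking, are defined by different movement. The amount of movement artifact may therefore differ between them, although the documents do not show that it does. If the reader also knows which segments are FOG, or which session was OFF medication, borderline windows could be judged differently by label.

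At stake is how far the reported FOG-walking difference in band power can be read as neural and how far it depends on which windows were kept. The study has no stated hypothesis test, so its credibility rests on how the descriptive summaries were built. The planned outputs would not show whether removal was balanced.

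**Working it through.** The plan gives no removal rate, artifact rate, effect size or SD, so there is no figure of its own to reproduce. The check has two parts: what the text commits to, and whether removal rates alone could tell us the bias.

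**1. The text, item by item**

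| Item | Stated for artifact removal? | Where |
|---|---|---|
| Criterion | Yes: two qualitative features | Neural Data Analysis |
| Numeric threshold | No | – |
| Reader masked to FOG/walking | No | – |
| Reader masked to medication state | No (stated only for the UPDRS rater) | Behavioral Tasks |
| Removal counts by event or state | No | – |
| Repeat under other cleaning | No | – |
| Event labels independent of the LFP trace | Yes: motion sensors | Biomechanical Data Analysis |

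The last row makes masking feasible. Labels that come from the sensors can be withheld while the LFP is reviewed. Describing removal before the spectrograms shows neither that the reader is masked nor that labels drive removal.

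**2. Do unequal removal rates fix the bias?**

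Every input here is assumed. Take no true difference, clean power with mean 1, and 20% of FOG windows against 5% of walking windows removed. These cases show dependence on the model and are not estimates for this trial.

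*Case A: the removed windows are ordinary ones with the highest power.* With exponential window power and top share f removed, the retained mean is 1 + f·ln(f)/(1−f).
- FOG, f = 0.20: 1 + 0.20 × (−1.609)/0.80 = 0.598
- Walking, f = 0.05: 1 + 0.05 × (−2.996)/0.95 = 0.842
- FOG/walking ratio: 0.598/0.842 = 0.71. With the rates reversed it is 1.41.

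*Case B: the removed windows are exactly the artifact windows.* The retained mean is 1 in both events, so the ratio is 1.00.

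*Case C: artifacts are discrete and detection is imperfect.* Let 20% of FOG windows and 5% of walking windows carry k times normal power. Each window has ten independent exponential frequency cells, and one shared threshold on total power is set between 18 and 22. Clean total power is Gamma(10). Roughly 16–21% of FOG windows and 4–6% of walking windows are then removed. The spurious difference left is at most about 3% at k = 3 and within about 0.3% at k = 5 or 10.

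Similar removal rates thus give anything from a large spurious difference in either direction to almost none. What decides it is whether the windows removed are artifact, which the rates alone do not show.

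**3. Would a run with no removal settle it?**

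Under Case C's artifact shares with nothing removed, the mean is 1 + g(k−1), where g is the artifact share.
- k = 3: (1 + 0.20 × 2)/(1 + 0.05 × 2) = 1.40/1.10 = 1.27
- k = 10: (1 + 0.20 × 9)/(1 + 0.05 × 9) = 2.80/1.45 = 1.93

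There is no true difference in this model and the cleaned contrast is close to correct, yet the no-removal run shows a large one. It puts known artifact back, so disagreement with it would not show that the cleaned result is wrong.

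**The case against.** The strongest reply is that this is ordinary preprocessing in a 15-person descriptive study. A criterion exists, with two features. Sensor-based labels mean that cleaning does not define the FOG episodes. Removing artifact usually lowers bias, and nothing says that raw traces are discarded, so windows can be counted or re-cleaned later.

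Most of that stands. The rule is subjective but not absent, and the step itself is reasonable. Sensor labels protect the definition of an episode, though not the choice of windows kept within it. Re-cleaning is possible for the study team, so a reader should not infer that the effect of cleaning can never be checked. The supportable statement is that it is not planned to be reported. With data access limited to the investigators, an outside reader depends on what they report.

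Two further inferences are tempting and are not supported:

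- **That masking the UPDRS rater but not the artifact reader is an internal contradiction.** It is not. One is a clinical rating and the other is signal processing. The contrast shows only that masking is stated for one judgement and not for the other.
- **That the ON-OFF comparison is distorted too.** It compares FOG with FOG. An effect is possible if removal differs by session, but nothing in the documents shows one.

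**Conclusion.** The point holds as a cheap improvement. Windows are dropped by visual judgement on features that overlap the outcome, no masking to event or medication state is stated, and the amount removed is not planned to be reported. Label-aware or unequal removal could move the descriptive FOG-walking contrast without being visible in the planned results.

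A reader might go further and conclude that the contrast will be biased, or biased in a known direction. The documents do not support that. They give no removal rate and no artifact rate, and the worked cases show that similar assumed rates are compatible with a sizeable spurious difference of either sign or with almost none. No magnitude should be attached to this point.

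The conclusion rests on the absence of any masking, count or repeat-analysis statement in the text as supplied, and on unequal movement artifact between freezing and walking being plausible rather than shown.

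**What to change.** 1. Keep the two-feature criterion as the main rule. Do the visual review on segments shuffled by script, with FOG/walking labels and session (medication) labels hidden.
2. Report the percentage of windows removed by event type and medication state, for each participant.
3. As one sensitivity run, repeat the FOG-walking contrast with a pre-set scripted broadband threshold applied equally to both events, and state whether the size or sign changes. This does not replace the main rule.
4. If a no-removal run is also shown, label it as a bound that contains known artifact, not as a test of the cleaned result.

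The cost is a little off-line scripting, one table and a few lines of SAP text, with no extra participants or visits. Masking limits label-driven discretion. It does not correct for movement artifact that truly differs between events, which is why items 2 and 3 go with it, and it may be imperfect if the gait rhythm is visible in the trace.
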